# 9.9 Randomisation

On Day 1 of each part, subjects in each cohort will be randomised to receive either C106 (n=6) or placebo (n=2). Subjects will be randomised in 2 blocks. The first 2 subjects in a cohort will be randomised to C106 (n=1) or placebo (n=1). The next subjects will be randomised in a 5:1 ratio to receive C106 (n=5) or placebo (n=1). A computer-generated randomisation list will be created using SAS Proc Plan, SAS Version 9.4. The randomisation list will contain subject number and treatment and will be kept by the randomiser in a sealed envelope until database lock. A copy of the randomisation list will be kept by an unblinded IMP preparation staff member at the site.

Sealed individual, treatment code envelopes will be kept at the clinic and at CTC's Pharmacovigilance department (CTC PV) in locked and restricted areas if needed for emergency unblinding.

# 9.10 Blinding

This is a double-blind trial, and the allocation of treatments will not be disclosed until clean file has been declared and the database has been locked.

The IMP, *i.e.*, the C106 and the placebo oral solutions, are identical in appearance. Both solutions are colourless to yellow. Hence, it is expected that the subjects, Investigator and other site personnel will remain unaware of treatment allocation.

# 9.11 Emergency unblinding during the trial

The treatment code may only be broken by the Principal Investigator or delegate in case of emergency when knowledge of the treatment received is necessary for the proper medical management of the subject. The code breaking procedure should be carefully documented.

## 9.11.1 Unblinding for other reasons than emergency

The treatment code may be broken by the iSRC during the assessment process (partial unblinding) to enable their decision on continued dosing of further cohorts or to stop the dose escalation. The medical staff and the subjects will still be blinded for the treatments (active drug or placebo) to be administered in the subsequent cohorts in order to minimise bias, see Section 8.3.6.

For unblinding procedures in case of a potential suspected unexpected serious adverse reaction (SUSAR), see Section 11.3.1.14.

# **10 TREATMENTS**

## **10.1 Identity of investigational medicinal products**

C106 is a potent and selective nonpeptide AT2R agonist developed by Vicore Pharma. C106 will be administered as an oral solution.

The bulk drug product will be provided to the research clinic as:

- C106 solution for oral administration; 1 mg/mL (25 mL solution in 30 mL amber vials) and 10 mg/mL (50 mL solution in 50 mL amber vials). Expressed as salt; equivalent to 0.955 mg/mL and 9.55 mg/mL of the free form.
- Placebo to C106 is a solution for oral administration, manufactured as the drug without the active pharmaceutical ingredient. Placebo will be provided in volumes of 50 mL (50 mL amber vials).

## 10.2 Manufacturing, packaging, labelling, and release

The IMP, including placebo, is manufactured, packaged, labelled, and released by Ardena, Ghent, Belgium.

Trained, unblinded clinical staff will prepare and label the IMP according to the randomisation schedule.

Labels will comply with applicable Good Manufacturing Practice (GMP), with Annex 13 of the European Union Good Manufacturing Practice regulations and local regulatory requirements.

The bulk IMP will be shipped to the research clinic (CTC).

## **10.3** Conditions for storage

The bulk drug product will be stored refrigerated at 2 to 8°C in an access-controlled storage area at CTC. The finally prepared in-use IMP can be stored at 2 to 8°C for a maximum of 24 hours.

Temperature logs will be kept for the area where the IMP is stored. The temperature should be noted on a daily basis (working days only unless automatic temperature readings are available).

The drug product must be protected from light.

## **10.4** Preparation and accountability

IMP preparation will be done by trained personnel, *i.e.*, a site pharmacist or a registered nurse, in a dedicated room at CTC. There will be two unblinded persons working together, one person will handle the IMP and perform the preparation according to the randomisation list and the other person will supervise the process. The personnel preparing the IMP will not be involved in any other trial activities.

CTC and the Investigator will maintain a Storage and Accountability Log as well as a Drug Dispensing Log detailing the dates and quantities of IMP received, prepared for and used by each subject and IMP returned or destroyed at the end of the trial. Any discrepancies between prepared and returned IMP must be explained and documented. Products deliberately and/or accidentally destroyed by the site or the subject must be accounted for.

# **10.5** Treatment administration

## 10.5.1 Treatment administration Part A

Subjects in Part A (SAD) will be administered a single oral dose of either C106 or placebo as randomised. The proposed doses are 5, 30, 60, 180, 240 and 300 mg C106.

Subjects who participate in the food interaction part will be administered a second single dose of either C106 or placebo. Any replacers in the food interaction part will receive C106 and will participate in both a fasting and a fed period.

## Part A fasting conditions

Following an overnight fast of at least 10 hours, subjects will be administered the IMP with approximately 240 mL of water (including the volume of the IMP). No food is allowed for at least 4 hours post dose. During fasting, water, but no other drinks, is allowed as desired. Water is allowed *ad libitum* at the clinic except 1 hour before dose and 1 hour after dose. The IMP will be taken with water (approximately 240 mL, including the volume of the IMP).

## Part A fed conditions (one cohort)

Following an overnight fast of at least 10 hours, subjects will start a high-fat, high-calorie meal 30 minutes prior to administration of the IMP (for details on the breakfast, see below). The subjects should eat this meal in 30 minutes or less, however, the IMP should be administered 30 minutes after start of the meal. No food is allowed for at least 4 hours post-dose. During fasting, water, but no other drinks, is allowed as desired. Water is allowed *ad libitum* at the clinic except 1 hour before dose and 1 hour after dose. The IMP will be taken with water (approximately 240 mL, including the volume of the IMP).

The high-fat, high-calorie breakfast will consist of the following (or equivalent): 2 eggs fried in butter, 2 strips of bacon, 2 slices of toast with butter, 4 ounces of hash brown potatoes (118 mL) and 8 ounces (236 mL) of whole milk. Substitutions in this meal can be made as long as the meal provides a similar number of calories from protein, carbohydrate, and fat and has comparable meal volume and viscosity. The test meal should derive approximately 150, 250, and 500-600 calories from protein, carbohydrate, and fat, respectively.

# 10.5.2 Treatment administration Part B

Subjects in Part B (MAD) will be administered oral doses of C106, or placebo as randomised for 8 consecutive days. The proposed doses are 40, 100, 180 and 240 mg BID for 8 days.

Subjects will be administered the IMP with approximately 240 mL of water (including the volume of the IMP) by clinical staff from Day 1 to 8, *i.e.*, at all dosing occasions.

The first IMP dose should be taken prior to breakfast and the second dose after 12 hours, on all treatment days. On Day 8, only the morning dose will be administered. Fasting is required 2 hours before and 1 hour after both the morning and evening dose.

## **10.6** Continuation of treatment with Investigational Medicinal Product

This is a Phase 1 trial in healthy volunteers who will have no medical benefit from the treatment and thus there will be no treatment with C106 after end of trial participation.

## **10.7** Treatment compliance

In both Part A and Part B, all IMP will be administered at the research clinic under medical supervision to ensure compliance.

## **10.8** Return and destruction of investigational medicinal products

Any unused trial medication and all empty containers will be destructed at the site upon confirmation from the Sponsor. The Monitor will perform final IMP accountability reconciliation at the trial end to verify that all unused IMP is adequately destroyed and documented.

# 11 TRIAL ASSESSMENTS

The trial assessments are described in the sections below and the timing of these assessments are detailed in the schedule of events (Table 8.1-1 and Table 8.1-2 for Part A and Table 8.1-3, Table 8.1-4 and Table 8.1-5 for Part B).

# 11.1 Recording of data

The Principal Investigator will provide the Sponsor with all data produced during the trial from the scheduled trial assessments. The PI ensures the accuracy, completeness, legibility, and timeliness of the data reported to Sponsor in the eCRF and in all required reports.

It is important that Cardiodynamic ECG and PK blood sampling occurs as close as possible to scheduled time. In order to achieve this, the timing priority order at a particular time point is:

## Part A (SAD):

- 1. Cardiodynamic ECG/Blood samples for PK
- 2. Safety laboratory samples
- 3. Safety 12-lead ECG
- 4. Vital signs

## Part B (MAD):

- 1. Blood samples for PK
- 2. PD assessment (cohort B4 only)
- 3. Safety laboratory samples
- 4. Safety 12-lead ECG
- 5. Vital signs

Time points for PK blood sampling, PD assessment (cohort B4 only), safety laboratory samples, 12-lead ECG, and vital signs are outlined in Table 8.1-1 and Table 8.1-2 for Part A and in Table 8.1-3, Table 8.1-4 and Table 8.1-5 for Part B.

For allowed time windows for PK samples, see Section 11.4.1.

## **11.2 Demographics and other baseline characteristics**

## 11.2.1 Informed consent

Signed informed consent must be obtained before any screening procedures are initiated. The informed consent procedure is further described in Section 14.3.

## 11.2.2 *Eligibility criteria*

Eligibility criteria should be checked during screening and verified before randomisation. The criteria are specified in Sections 9.4 and 9.5.

## 11.2.3 Demographic information

The following demographic data will be recorded: gender, age, ethnicity, and race.

# 11.2.4 Weight and height

Weight and height will be measured without shoes. BMI will be calculated, with one decimal, from the height and weight recorded.

# 11.2.5 Medical/surgical history

Medical/surgical history will be obtained by subject interview in order to verify that the eligibility criteria are met.

The medical/surgical history should include all relevant diseases and surgeries prior to screening as judged by the Investigator.

# 11.2.6 Prior and concomitant medication

Prior medications taken within 2 weeks will be obtained by subject interview in order to verify that the eligibility criteria are met (see also Section 9.6.2).

Medications are classified as prior if the stop date was before or on the day of the first dose administration (pre-dose) and as concomitant if ongoing on the day of the first dose administration, stopped after the first dose administration or started after the first dose administration. To distinguish between prior and concomitant medications on Day 1 in each part (*i.e.*, the first dosing day), the start time of any newly introduced medication or the stop time of any previously ongoing medication must be recorded in the eCRF.

Any use of concomitant medication from screening until the last end-of-trial visit must be documented appropriately in the subject's eCRF. Relevant information (*i.e.*, name of medication, dose, dose form, unit, route, frequency, start and stop dates, reason for use) must be recorded. All changes in medication should be noted in the eCRF.

# 11.2.7 HIV and Hepatitis B/C

[figure not shown]
Subjects will be tested for HIV-1 and HIV-2 antibodies and HIV-1 p24 antigen, hepatitis B virus surface antigen and hepatitis C virus antibodies prior to inclusion into the trial. Any positive result will exclude the subject from participating in the trial.

# 11.2.8 Urine drug screen

Urine will be screened for drugs of abuse at time points outlined in the schedule of events (Table 8.1-1 for Part A and Table 8.1-3 for Part B) using the Drug Screen Multi-12/15 Dip Test (Nal von minden) or equivalent. Additional random tests can be performed during the trial period.

# 11.2.9 Alcohol test

An alcohol test will be performed at time points outlined in the schedule of events (Table 8.1-1 for Part A and Table 8.1-3 for Part B). Additional random tests can be performed during the trial period.

# 11.3 Assessments related to primary endpoints

## 11.3.1 Adverse events

The Principal Investigator is responsible for ensuring that all medical staff involved in the trial is familiar with the content of this section and the content of the CTC standard operating procedures (SOPs) regarding emergencies and FIH studies.

# 11.3.1.1 Definition of adverse event

An AE is defined as any untoward medical occurrence in a subject administered a medicinal product and which does not necessarily have a causal relationship with this treatment. An AE can therefore be any unfavourable and unintended sign (including an abnormal laboratory finding), symptom, or disease temporally associated with the use of a medicinal product, whether or not considered related to the medicinal product.

## 11.3.1.2 Definition of serious adverse event

An SAE is any AE which:

- results in death
- is life-threatening (this refers to a reaction in which the subject was at risk of death at the time of the reaction; it does not refer to a reaction that hypothetically might had led to death if the reaction was more severe)
- requires in-subject hospitalisation or prolongation of existing hospitalisation
- results in persistent or significant disability/incapacity
- is a congenital anomaly/birth defect
- is an important medical event (IME) (this refers to a reaction that may not be immediately life-threatening or result in death or hospitalisation, but may jeopardise the subject or may require intervention to prevent any of the other outcomes defined above)

Examples of IMEs are intensive treatment in an emergency room for allergic bronchospasm or blood dyscrasias, convulsions that do not result in hospitalisation, development of drug dependency, and drug abuse.

Planned hospitalisations or surgical interventions for a condition that existed before the subject signed the ICF and that did not change in intensity are not SAEs.

If there is any doubt as to whether an AE meets the definition of an SAE, a conservative viewpoint must be taken, and the AE must be reported as an SAE.

# 11.3.1.3 Definition of adverse drug reaction

The term adverse reaction is to be used for all untoward and unintended responses to the IMP assessed as related to any dose administered.

## 11.3.1.4 Definition of serious adverse drug reaction

The term serious adverse reaction (SAR) is to be used whenever either the Investigator or Sponsor or designee assessed the SAE as related to the IMP.

## CONFIDENTIAL

# 11.3.1.5 Definition of suspected unexpected serious adverse reaction

A SUSAR is any SAE that has a suspected causal relationship with the IMP (assessed as related by the Sponsor or Investigator), but the nature of which is not consistent with the applicable product information (*i.e.*, the IB).

# 11.3.1.6 Time period and frequency for collecting adverse events

All AEs (including SAEs) will be collected from the signing of informed consent until the end-of-trial visit of each part.

Any AE with start date on the day of IMP administration must be recorded with start time.

At the end-of-trial visit, information on new AEs or SAEs, if any, and stop dates for ongoing events must be recorded as applicable.

Investigators are not obligated to actively seek AEs or SAEs after conclusion of the trial participation. However, if the Investigator learns of any SAE, including a death, at any time after a participant has been discharged from the trial, and he/she considers the event to be reasonably related to the trial intervention or trial participation, the Investigator must promptly notify the Sponsor.

# 11.3.1.7 Assessment of intensity

The grading of the intensity of AEs will follow the CTCAE v5.0 [40]. Grade refers to the severity of the AE. The CTCAE displays Grades 1 through 5 with unique clinical descriptions of severity for each AE based on this general guideline.

The Investigator must assess the intensity of an AE using the following definitions, and record it on the AE Log in the eCRF:

- **Grade 1** Mild; asymptomatic or mild symptoms; clinical or diagnostic observations only; intervention not indicated.
- **Grade 2** Moderate; minimal, local or non-invasive intervention indicated; limiting ageappropriate instrumental activities of daily living (ADL)\*.
- **Grade 3** Severe or medically significant but not immediately life-threatening; hospitalisation or prolongation of hospitalisation indicated; disabling; limiting self- care ADL\*\*.
- Grade 4 Life-threatening consequences; urgent intervention indicated.

**Grade 5** Death related to AE.

\*Instrumental ADL refer to preparing meals, shopping for groceries or clothes, using the telephone, managing money, etc.

\*\*Self- care ADL refer to bathing, dressing and undressing, feeding self, using the toilet, taking medications, and not bedridden.

# 11.3.1.8 Assessment of causal relationship

The Investigator must assess the causal relationship between an AE and the IMP using the definitions below and record it the AE Log of the eCRF:

Related	There is a reasonable possibility that the AE was caused by the drug. There is a reasonable time relationship to drug intake. The AE cannot be explained by disease or other drugs. There may or may not be information about de- challenge or re-challenge. Disappearance of the AE upon de-challenge supports this category. Reappearance upon re-challenge is strongly supportive.
Not related	There is no reasonable possibility that the event was caused by the IMP. The temporal relationship to drug administration makes a causal relationship improbable or other drugs or underlying disease or conditions provide plausible explanations.
Not	This assessment can be used e.g. , in cases where the subject did not

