C106 has been generally well tolerated, without clinically significant findings regarding AEs, ECG, safety laboratory assessments and physical examinations. In total 2 AEs have been reported as possibly related to blinded IMP, both were transient and mild in intensity. In conclusion, the overall safety and tolerability evaluation has not identified any safety signals in the completed cohorts.

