# 8.3.5 Stopping criteria for dose escalation

The Principal Investigator and the iSRC (Section 8.3.6) will follow the recommendations and grading system of CTCAE v5.0 [40] see Section 11.3.1.7 but also take into account the recommendations published by Sibille *et al.* 2010 [41], which is an adaptation to FIH studies of the grading systems previously proposed by National Cancer Institute (NCI) [1], World Health Organisation (WHO) [42], National Institute of Health (NIH) [43] and the US Food and Drug Administration (FDA) [44]. The grade, the frequency of AEs and the blindness will be considered.

A rolling review of emerging safety data will be performed throughout the trial taking into account any AEs, the number of subjects in whom they occur, concurrency of more than one event within the same subject and any trends. Changes from baseline measurements will also be considered and not just absolute cut-off based on upper- or lower limits of normal that might apply for healthy volunteers.

Trends or safety signals, which are not necessarily covered by the stopping criteria in Table 8.3-3 and Table 8.3-4 may warrant the scheduling of *ad hoc* iSRC meetings after which the iSRC will make recommendations to the Sponsor on e.g. whether to terminate the trial or to stop dosing in individual subjects or a certain cohort.

Additional withdrawal criteria are summarised in Section 9.8.

	Stop criterion	Action taken
	At individual and dose group level	
1	If 1 on active treatment subject has an SAE assessed as related to IMP administration	1. Stop dosing of subject with a potential serious adverse reaction (SAR). Await dosing of additional subjects until the iSRC's recommendation and the Sponsor's decision on continuation.
		2. Unblinding of subject with potential SAR. Only voting members of the iSRC will be unblinded.
		3. Evaluation by iSRC. The iSRC makes recommendation to Sponsor.
		4. Sponsor decides how to proceed:
		The subject received active treatment, i.e., met stopping criterion: stop further dosing at this dose level for all subjects. Sponsor decides if the trial will be terminated or if dosing will resume at a lower dose level.
2	If 2 subjects on active treatment in the same cohort have severe, non-serious AEs assessed as	1. Stop dosing of subjects with severe, non-serious potential adverse reactions. Await dosing of additional subjects until the iSRC's recommendation and the Sponsor's decision on continuation.

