## Table 8.3-3 Dose escalation and stopping rules in Part A (SAD)

 When reviewing emerging data in relation to this criterion, the maximum exposure observed in individual subjects within a cohort rather than the mean exposure should be taken into account. The exposure predictions are normally based on the highest observed Cmax and AUCinf/AUCtau in the previous conducted SAD cohort assuming linear kinetics. If non-linear PK is observed in previously conducted cohorts, this will also be considered.

Stop criterion	Action taken
At individual and dose group level	
If 1 subject on active treatment has an SAE assessed as related to IMP administration	
 
Stop dosing of subject with a potential serious adverse reaction (SAR). Await dosing of additional subjects until the iSRC's recommendation and the Sponsor's decision on continuation.
 
Unblinding of subject with potential SAR. Only voting members of the iSRC will be unblinded.
 
Evaluation by iSRC. The iSRC makes recommendation to Sponsor.
 
Sponsor decides how to proceed: The subject received active treatment, i.e., met stopping criterion: stop further dosing at this dose level for all subjects. Sponsor decides if the
 

If 2 subjects on active treatment in the same cohort have severe, non- serious AEs assessed as related to the IMP administration (independent of within or not	
 
trial will be terminated or if dosing will resume at a lower dose level.
 
1. Stop dosing of subjects with severe, non-serious potential adverse reactions. Await dosing of additional subjects until the iSRC's recommendation and the Sponsor's decision on continuation.
 
2. Unblinding of the subjects with potential adverse reactions. Only voting members of the iSRC will be unblinded.
 

within the same System organ class [SOC])	
 
3. Evaluation by iSRC. The iSRC makes recommendation to Sponsor.
 
4. Sponsor decides how to proceed:
 
Both subjects received active treatment, i.e., met stopping criterion: stop further dosing at this dose level for all subjects. Sponsor decides if the trial will be terminated or if dosing will resume at a lower dose level.
 

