# 9.8.5 Subject replacement

Subjects who are prematurely withdrawn from the trial for any reason except the occurrence of AEs assessed as possibly or probably related to trial treatment may be replaced during the course of the trial.

Part A (SAD): subjects who are randomised but not dosed will be replaced. Subjects who are dosed will not be replaced.

In the event of dropouts in the fed cohort, subjects may be replaced to guarantee a full cohort size for the food-interaction part of the trial. Any replacers will receive active treatment both in the fasted and fed state.

Part B (MAD): Subjects who are randomised but not dosed will be replaced. Subjects who were prematurely withdrawn from the trial for any reason except the occurrence of AEs assessed at least possibly related to the IMP may be replaced.

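### The Related and Not related definitions in 11.3.1.8 conflict for AEs with both a reasonable drug cause and a plausible alternative, so it is ambiguous which events count toward the related-AE stopping rules

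*Combined protocol and SAP*

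**What the plan says.** Section 11.3.1.8 requires the Investigator to score causality in the eCRF as *Related*, *Not related* or *Not applicable*. The last is for cases such as a subject who received no IMP.

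- *Related* begins "There is a reasonable possibility that the AE was caused by the drug". It then asks for reasonable timing, and its third sentence reads "The AE cannot be explained by disease or other drugs". The remarks on de-challenge and re-challenge that follow are worded as optional or supportive.
- *Not related* begins "There is no reasonable possibility that the event was caused by the IMP". Its second sentence is met by improbable timing or, alternatively, when "other drugs or underlying disease or conditions provide plausible explanations".

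The AE-based stopping rules depend on relatedness. The first rule in Part A (Table 8.3-3) reads "If 1 on active treatment subject has an SAE assessed as related to IMP administration", and its Part B counterpart (Table 8.3-4) reads "If 1 subject on active treatment has an SAE assessed as related to IMP administration". The rules on severe non-serious AEs, on grade 2 hair loss (Part B only) and on SAEs in different cohorts carry the same condition.

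Other sections use a finer scale. Section 9.8.5 allows replacement after withdrawal for "any reason except the occurrence of AEs assessed as possibly or probably related to trial treatment", and its Part B paragraph sets the bar at an event that is at least possibly related. Section 6.1.7 reports "In total 2 AEs have been reported as possibly related to blinded IMP".

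**The concern.** A two-level scale is an ordinary choice and is not the problem. The problem is that the two levels do not divide events cleanly. One sentence in *Related* shuts out events that have another explanation, while the opening sentence of *Not related* shuts out events that the drug may reasonably have caused. An event with both features has no unambiguous place, and there is no middle category to hold it.

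Such events are foreseeable here. Section 9.6.2 permits paracetamol and nasal decongestants, so minor intercurrent illness is expected. Section 6.1.7 names headache as the most common treatment-related AE in the Phase 1 trials of the analogue C21. A severe headache soon after dosing in a subject who also has a cold would be a case in point.

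Two careful investigators could therefore score the same event oppositely, each with support in the text. In a first-in-human dose escalation, that score helps decide whether dosing pauses for iSRC review and unblinding.

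**Working it through.** No figure in the plan bears on this point, so the check sets the texts side by side.

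**Step 1. Test the four possible kinds of AE against both definitions** (timing taken as reasonable).

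| Drug cause reasonably possible? | Plausible alternative? | *Related* | *Not related* |
|---|---|---|---|
| Yes | No | Met | Not met |
| No | Yes | First sentence fails | Met |
| No | No | First sentence fails | First sentence met |
| Yes | Yes | First sentence met, third fails | First sentence fails, alternative-explanation limb met |

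Only the last row conflicts. The third sentence of *Related* cannot easily be read as merely supportive. Where that definition means supportive, it says so (de-challenge and re-challenge), and this sentence carries no such qualifier.

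**Step 2. Trace where the score is used.**

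| Use | Threshold | Second assessor named? |
|---|---|---|
| Related SAE (Tables 8.3-3, 8.3-4) | 1 subject | Yes: Sponsor or designee (11.3.1.4), Medical Monitor (11.3.1.14) |
| Related severe non-serious AE (both tables) | 2 subjects in a cohort | No |
| Related grade 2 hair loss (Table 8.3-4) | 2 subjects in a cohort | No |
| Related SAEs in different cohorts (both tables) | 2 subjects | Yes, as for SAEs |
| Follow-up of severe non-serious AEs after participation ends (11.3.1.15) | Each event | No |
| Relationship in the AE overview, and the related-AE summary if produced (17.5.1) | Not applicable | No |

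For SAEs, the documents do not spell out how a Sponsor or Medical Monitor judgement enters the stopping tables, although the listed actions refer to a potential serious adverse reaction.

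**Step 3. Compare the vocabularies.** The grades in 9.8.5 and 6.1.7 are absent from 11.3.1.8. The Part B bar in 9.8.5 maps naturally onto *Related* if reasonable possibility decides. If the third sentence of *Related* decides, a possibly related AE with an alternative explanation would be recorded as *Not related*, and the mapping fails.

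**Step 4. Sensitivity of a two-subject rule (illustration only).** Six subjects per cohort receive C106 (9.3). Let p be the per-subject rate of a qualifying drug-caused event, and q the share of those scored *Not related* because of a plausible alternative. Both are assumptions. With π = p(1 − q), taking subjects as independent:

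P(at least 2 scored related) = 1 − (1 − π)^6 − 6π(1 − π)^5

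For p = 0.2 and q = 0: 1 − 0.262 − 0.393 = 0.345.

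| p | q = 0 | q = 0.25 | q = 0.5 | q = 0.75 |
|---|---|---|---|---|
| 0.1 | 0.114 | 0.069 | 0.033 | 0.009 |
| 0.2 | 0.345 | 0.224 | 0.114 | 0.033 |
| 0.3 | 0.580 | 0.406 | 0.224 | 0.069 |
| 0.5 | 0.891 | 0.726 | 0.466 | 0.167 |

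The table shows what downgrading would do if it occurred. It is not evidence that it occurs: q could be 0.

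**The case against.** The strongest reply is that the lead sentences settle the matter. *Not related* requires no reasonable possibility, so an event that C106 may reasonably have caused cannot belong there. This defeats a stronger reading that a reader might infer, namely that the scale forces every possibly drug-caused AE into *Not related*. The text compels no such score, and a possible AE with reasonable timing and no alternative explanation is *Related* on any reading. The reply does not remove the conflict, because the third sentence of *Related* is equally part of the definition.

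Second, other safeguards exist. SAEs can be judged related by the Sponsor, its designee or the Medical Monitor. Section 8.3.5 provides rolling review of all AEs and allows ad hoc iSRC meetings on signals outside the rules. Section 8.3.6 has the iSRC consider any indication of hair loss after the 48-hour cut-off, whatever its cause. The individual liver criteria in 9.8.3 do not use the IMP causality score. So an event scored *Not related* does not necessarily escape attention or drop out of every rule. This stands, but rolling and ad hoc review is discretionary, and no second causality assessor is named for the severe non-serious AE and hair-loss rules.

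Third, healthy subjects under tight medication limits will have few competing explanations, and the primary safety tables include all AEs. Both points are fair and limit the reach of the problem.

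**Conclusion.** The concern holds as an inconsistency between stated rules. For AEs with both a reasonable drug cause and a plausible alternative, 11.3.1.8 supports either score. It is therefore ambiguous which events count toward the related-AE stopping rules, the follow-up rule in 11.3.1.15 and any related-AE summary. With thresholds of 1 or 2 subjects, the score given to a single event can decide whether a rule is met. The exposure is most direct for severe non-serious AEs and hair loss.

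The extent of any misclassification cannot be estimated, because no document gives the share of AEs with a competing explanation. Two inferences should be avoided:

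- **A demonstrated downward bias.** The wording leaves room for one, but nothing shows that it has happened.
- **A fall in the related count from 2 to 0 for the AEs in 6.1.7.** That would need both to have had a plausible alternative, which is not stated. Both were transient and mild, so neither could have met an AE stopping rule, and both were in fact reported as possibly related.

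The mismatch with 9.8.5 is one of terminology. The replacement rule remains usable once the mapping is stated.

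**What to change.** Reconcile the passages as follows.

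1. **Section 11.3.1.8.** Make reasonable possibility of causation by the IMP the single deciding test: present for *Related*, absent for *Not related*. Recast alternative explanations as supporting evidence, neither disqualifying for *Related* nor sufficient alone for *Not related*.
2. **Section 9.8.5.** Replace the graded terms with the recorded category, so that replacement can be decided from the eCRF field.
3. **AEs already described as possibly related.** State how they map to the two-level scale, including the two in 6.1.7.

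This takes a few words in an amendment and in the eCRF completion guidance. It alters no dose and no stopping threshold. The cost is that slightly more AEs will be classed as related, so a relatedness-based rule may be met somewhat more readily.
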